## 2.4 Blinding

Each site PI will be able to unblind an individual subject. The blinding should only be broken in case of an emergency, and only if the knowledge obtained through the unblinding is assessed to be needed for the proper treatment or continued safety of the subject experiencing the emergency.

The pharmacovigilance responsible CRO will be able to unblind an individual subject prior to submitting an expedited report of a suspected unexpected serious adverse reaction (SUSAR) to a CA or IEC, if unblinding is required by the CA or IEC.

Whenever possible, the sponsor, MinervaX, should be consulted before the blind is broken by the site.

The unblinding of a subject by the site PI or the pharmacovigilance responsible CRO takes place through the unblinding module in the eCRF, to which the applicable parties will be given access.

If unblinding of a subject has taken place (intentionally or unintentionally), the sponsor must be informed immediately, and be provided with an explanation, and it must be considered to withdraw the unblinded subject from the study.

The information in this section is described in more detail in a study specific blinding manual.

During conduct of the study an unblinded DSMB will work independently from the blinded study team. Likewise, an interim/early efficacy analysis focused on unblinded immunogenicity data, and certain key safety data, will be conducted when Visit 8 has been completed for the last subject (baby). These activities involving unblinded personnel are described in further detail in section 6 below.

## 2.5 Randomization

In accordance with Table 1 above, patients are randomized into groups 1 to 5 using the allocation ratio 2:2:2:2:1. This is achieved by stratifying randomization on site (10 sites) and, within site, using blocking of size 9 with each block containing two occurrences of a given active group (1 to 4) and one occurrence of placebo (group 5) in random order. The assignment of group to any new eligible patient occurs through the eCRF in such a way that blinded staff will have access to the randomization date and number only. The randomization list is prepared and uploaded to the eCRF system by a statistician who remains in an unblinded role throughout the blinded part of the study.

## 2.6 Data pre-processing

The data processing chain from the raw data received from data management to End-of-Text documents contains steps to convert data from electronic case report form (eCRF) modules and external data sources, into datasets compliant with Clinical Data Interchange Standards Consortium (CDISC) standards. The first step of the process converts data into standardized CDISC Study Data Tabulation Model (SDTM) domains.

In the second step of the process, the SDTM domains are used to produce standardized CDISC Analysis Data Model (ADaM) datasets. In the third step, the table, listing, and figure (TLF) elements are produced from the ADaM datasets. In the final step, the TLF elements are collected and stored in End-of-Text (EOT) documents.

## 3 Analysis sets

In this section, the different analysis sets to be used for statistical analysis are presented. Each subject will be classified according to the definitions below at blinded data review meetings. The classification and related decisions will be made by the study team and documented in the minutes from the meeting. The Baby Immunogenicity Set (BIG) and Baby Per Protocol Set (BPP) refer to the babies born to study subjects.

All safety analyses will be performed on the Safety Analysis Set (SAF) and analysed according to the actual treatment received (treatment arms 1 to 5). All Immunological analyses will be performed on the Maternal Immunogenicity Set (MIG) and BIG sets. The primary immunological analysis (i.e., the immunogenicity results at delivery) will also be performed on the BPP set. These analyses will be based on randomised treatment.

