### 4.3.3 Safety assessments

The safety of the GBS-NN/NN2 vaccine will be assessed through collection of adverse events (AEs) in electronic diaries up to 7 days following each administered vaccination, as well as through laboratory safety tests, physical examinations and vital signs performed at the study visits. The safety assessments at the study visits cover both the mother and the baby.

AEs in the mother are assessed from the time the informed consent is signed until Day 84. From Delivery (Visit 8) and onwards, only MAAEs, AEs of special interest (AESI), e.g., GBS disease, autoimmune disease and immune-mediated reactions, or SAEs are assessed.

Any participant found to be pregnant at the end of the study will be followed up, as regards if their baby is healthy at delivery.

For the babies, all AEs will be assessed for the first 28 days of life, after this only MAAEs, AESIs e.g., GBS disease, abnormal development according to developmental milestones, or SAEs.

For further details, see Table 2 for mothers, and Table 3 for babies.

AEs with onset before the first administration of investigational product in a subject are defined non-treatment emergent AEs, and AEs with onset after the first administration of investigational product are defined treatment emergent AEs.

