## 6 Safety procedures

This section of the protocol defines periodic and expedited adverse event (AE) reporting obligations of the investigators.

Definitions and terms follow ICH E6 (R2) and Directive 2001/20/EC (to be replaced by Regulation (EU) 536/2014 when implemented).

In this study, adverse events (AEs) will be collected from the time of signing the informed consent form. AEs with onset prior to the first administration of GBS-NN/NN2 or placebo, will be designated non-treatment-emergent AEs where AEs with onset after the first administration of vaccine will be designated treatment emergent AEs.

The investigator is responsible for the detection and documentation of events meeting the criteria and definition of an AE or serious adverse event (SAE), as provided in this protocol. During the study when there is a safety evaluation, the investigator or site staff will be responsible for reporting AEs and SAEs.

The information in this section will, if applicable, be described in more detail in a study specific pharmacovigilance management plan.

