## 6.4 Reporting of adverse events including SAEs, MAAEs and AESIs

AEs will be reported in the eCRF pages from informed consent until the subject has completed/is withdrawn from the study (including any follow-up period), see details in Table 2 for mothers and Table 3 for babies.

Adverse events identified from the e-diaries will be transferred to the AE form in the eCRF, if they meet the following criteria:

- Any unsolicited AE
- Solicited local or systemic reaction to be assessed for the subject's withdrawal from study or study vaccine
- Solicited local or systemic reaction, rated by the subjects in the eDiary, categorized as severe
- Solicited local or systemic reaction lasting beyond 7 days from the day of vaccination
- Solicited local or systemic reaction that meets the definition of a SAE

Solicited local or systemic reactions are per definition regarded as related to the study vaccine, and the intensity is defined as described in section 6.1.

All maternal SAEs, as well as medically attended adverse events (MAAEs) and AEs of special interest (e.g., GBS disease, autoimmune diseases and immune-mediated reactions) will be reported from the day of signing informed consent for study participation and until the end of the study (Visit 11).

All baby SAEs, as well as MAAEs and AESIs (e.g., GBS disease, abnormal development according to developmental milestones), will be reported from birth up to 180 days post-delivery (Visit 11).

All SAEs, and AESIs, occurring from the time of signing the informed consent form until the subject has completed the study will be reported by completing and sending the SAE form (via email, or if required, via fax) to the pharmacovigilance provider (contact details below) within 24 hours of awareness / learning about the event i.e., within 24 hours after the investigator becomes aware that the event meets the protocol definition of a SAE.

SAEs occurring after study termination must be reported if considered related to the study drug.

After the initial SAE report, the investigator is required, proactively, to provide further information regarding the subject's condition.

In case of a fatal or life-threatening suspected unexpected serious adverse reaction (SUSAR), relevant follow-up information should be forwarded immediately.

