## 4.7 Analysis of safety (key secondary endpoint)

### 4.7.1 Adverse events

AEs relating to mothers (study subjects) will be coded using the latest available version of MedDRA. An overall summary table will be provided showing the number and percentage of subjects, within the SAF analysis set, with any:

- Treatment-emergent adverse events (TEAEs)
- Severe TEAEs
- Vaccine related TEAEs
- Vaccine related severe TEAEs
- Treatment-emergent SAE
- Treatment-emergent vaccine related SAEs
- TEAEs leading to withdrawal
- TEAEs with outcome death

The frequencies of the following key secondary safety endpoints will be tabulated in descriptive frequency tables:

- Treatment-emergent solicited injection site reactions
- Treatment-emergent solicited systemic AEs
- All treatment-emergent AEs
- For solicited events and reactions the summary tables will furthermore be presented by vaccination number/visit.

Treatment emergent AEs will be tabulated by system organ class and preferred term and treatment using the latest MedDRA coding.

All treatment emergent events will be listed. Non-treatment emergent events (if any) will be listed separately.

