#### 4.8 Analysis of weight of infant (exploratory endpoint)

Weight of the infant is not considered an endpoint in the protocol. It is however measured on four occasions and since weight of newborns is generally considered of medical importance weight will be made, comparing the 5 treatment groups (including group 5). The change-from-baseline (birth) in infant weight will be analyzed using a simple random effects model. Pseudo code related to the implementation of this model:

```
proc mixed data = weight data;  
  class subject group visit region;  
  model change_weight = birth_weight region group*visit / ddfm=sat;  
  random intercept / subject=subject;  
  lsmeans group*visit / diff cl obsmargins;run;
```

*Change\_weight* is the change from baseline in weight and *visit* is the study Visit (i.e., 9, 10, 11). Least square mean estimates of change from baseline in weight with 95% confidence intervals (CI) will be presented at each visit for each vaccination group. Estimated group differences at visit 11 between vaccination groups along with associated 95% confidence intervals and p-values will be presented. Estimated least square means and associated 95% CI of change from birth weight will be plotted over time, by vaccination group.

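### A low-cost addition: compare adverse events after the first injection between the 120 women randomised to vaccine and the 150 randomised to saline, with a confidence interval

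*SAP*

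**What the plan says.** Safety and tolerability of the vaccine is the key secondary objective (protocol 3.2). SAP section 3 has safety "analysed according to the actual treatment received (treatment arms 1 to 5"). SAP 4.7.1 gives counts and percentages of mothers with any, related, severe or serious TEAE, and adds: "Treatment emergent AEs will be tabulated by system organ class and preferred term and treatment using the latest MedDRA coding". The split by injection is limited to solicited events: "For solicited events and reactions the summary tables will furthermore be presented by vaccination number/visit". SAP 4.1 also asks for adverse event tables pooled over all sites and separately for South Africa and Europe. It has a general sentence that analysis results carry estimates, 95% confidence intervals and p-values, but it names no adverse event comparison. The protocol synopsis states that safety is summarised descriptively.

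On timing, protocol section 6 says: "AEs with onset prior to the first administration of GBS-NN/NN2 or placebo, will be designated non-treatment-emergent AEs". The treatment-emergent period therefore opens at the first injection of either product. Protocol 4.3.3 adds: "AEs in the mother are assessed from the time the informed consent is signed until Day 84". For serious, medically attended and special-interest events in mothers, protocol 6.4 says they "will be reported from the day of signing informed consent for study participation and until the end of the study (Visit 11").

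On allocation, SAP 2.5 describes site-stratified blocks of nine, "each block containing two occurrences of a given active group (1 to 4) and one occurrence of placebo (group 5) in random order".

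**The concern.** The only all-saline arm has 30 women, so any informal comparison of a vaccine arm with Group 5 is imprecise. Yet at Visit 1 the women of Groups 1 and 4 also receive saline. They are randomised controls for the first vaccine dose given to Groups 2 and 3, with no earlier study vaccine and therefore no carry-over. Protocol 6.7 uses this split to describe the first DSMB review, but the SAP does not use it for reporting.

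The specified tables do not supply the comparison for unsolicited events. In Groups 1 and 4 the first four weeks or so are saline time, but TEAEs from those weeks are counted in a vaccine arm and are not shown separately. First-injection counts of unsolicited, related, severe or serious TEAEs would have to be rebuilt from listings. At stake is the precision of the first-dose safety estimate for a vaccine given in pregnancy, in a trial whose safety results feed the choice of regimen for phase III.

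**Working it through.** **Inputs.** Group sizes 60, 60, 60, 60, 30 and the product at each visit: protocol Table 1 and SAP Table 1. Blocks of nine: SAP 2.5. Visit 3 (second injection) at Day 26 to 30: protocol Table 2. Full maternal AE collection to Day 84: protocol 4.3.3. About 18 weeks from 22 weeks' gestation to delivery: protocol 4.9. Visit 11 at 166 to 194 days post-delivery: protocol Table 2. The documents give no adverse event rates, so the rates below are assumptions shown as a range.

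**Step 1: the plan's own figure.** Vaccine at Visit 1: Groups 2+3 = 60 + 60 = 120. Saline at Visit 1: Groups 1+4+5 = 60 + 60 + 30 = 150. Among the first 27 women, 27 × 120/270 = 12 and 27 × 150/270 = 15, which reproduces the 12/27 and 15/27 in protocol 6.7. Each complete block holds 2 + 2 = 4 vaccine-first and 2 + 2 + 1 = 5 saline-first women, so the comparison is balanced within complete site blocks.

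**Step 2: saline time counted in vaccine arms (Groups 1 and 4).** Of full AE collection: 28/84 = 33% (26/84 = 31% to 30/84 = 36% with the Visit 3 window). For serious TEAEs, follow-up is about 126 + 166 = 292 to 126 + 194 = 320 days, so the share is 28/320 = 8.8% to 28/292 = 9.6%.

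**Step 3: precision at the same injection.** Half-width = 1.96 × √[p(1−p)(1/n₁ + 1/n₂)].

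| Assumed event rate | 120 vs 150 | 120 vs 30 (Groups 2+3 vs Group 5) |
|---|---|---|
| 5% | 5.2 points | 8.7 points |
| 10% | 7.2 points | 12.0 points |
| 20% | 9.6 points | 16.0 points |

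The ratio does not depend on p: 1/120 + 1/150 = 0.0150 and 1/120 + 1/30 = 0.04167, so √(0.0150/0.04167) = 0.60. The interval is 40% narrower.

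**Step 4: difference detectable with 80% power.** This is the smallest increase for which the exact binomial probability that the lower 95% Newcombe-Wilson limit exceeds zero reaches 80%, searched in steps of 0.1 point.

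| Saline rate | 120 vs 150 | 120 vs 30 |
|---|---|---|
| 5% | 10.0 points | 21.0 points |
| 10% | 12.1 points | 23.8 points |
| 20% | 15.2 points | 26.8 points |
| 30% | 16.6 points | 27.6 points |

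At saline rates of 1 and 2%, 120 vs 150 still needs 6.7 and 7.8 points.

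**Step 5: interaction with date imputation.** SAP 4.2 sets a completely missing AE start date to the treatment start date. It does the same when the month is missing and the year is that of first dosing, and otherwise takes the earliest compatible date after first vaccination. This is harmless for whole-study tables. In a table by injection period, it could place an undated event that followed vaccine in the saline period of Groups 1 and 4. The documents do not say how often dates are incomplete.

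**The case against.** **Descriptive safety reporting is a stated choice.** This stands: the point is an improvement, not a defect. A reader might infer that the by-arm tables are biased because Groups 1 and 4 include pre-vaccine time. The documents do not support that. Every arm has the same injection schedule and the same AE rules, so the tables are a valid comparison of regimens, which is the trial's purpose.

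**Other breakdowns exist.** They do: the pooled and regional AE tables and the general interval sentence in SAP 4.1. None separates first-injection vaccine from saline for unsolicited events or defines an AE difference. SAP 4.8 does estimate group differences, "comparing the 5 treatment groups (including group 5"), but for infant weight only.

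**Part of this is already available.** For solicited reactions, the 120 and 150 counts can be summed from the planned tables by vaccination number. TEAEs and exposure are also listed, so single events can be traced to an injection. The new content is the unsolicited events and the intervals. The DSMB looks at first-injection events with 28 days of follow-up, but in 27 women.

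**The shells may contain it.** SAP section 10 keeps them in a separate document that was not seen. The finding is limited to what the protocol and SAP specify.

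**The gain is narrow.** This also stands. A reader might carry the gain over to all vaccine arms against Group 5. That would set a four-week, first-dose window against a whole-regimen comparison whose event rates need not match. The fair comparator is 120 vs 30 at the same injection.

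**Conclusion.** Worth considering as a cheap improvement; nothing in the planned tables needs correcting. Neither the protocol nor the SAP specifies a vaccine-minus-saline adverse event difference with a confidence interval, although Visit 1 provides a randomised comparison of 120 with 150 that the protocol itself recognises. Using it makes the first-dose interval 40% narrower than relying on Group 5 alone, whatever the event rate. The half-widths and detectable differences rest on the assumed rates and on full group sizes at Visit 1.

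The comparison describes a first dose at about 22 weeks' gestation over about four weeks. It says nothing about second doses or delivery outcomes, and adds little for rare serious events. It is sound only with an explicit rule for incomplete onset dates.

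**What to change.** Keep all existing tables, the causality assessment and the regimen comparison. Add to SAP 4.7.1, as descriptive supplementary analyses:

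1. **First-injection comparison.** Safety set, by product actually injected at Visit 1 (as randomised, Groups 2+3 vs Groups 1+4+5), listing women who did not receive their randomised product. Outcomes: at least one solicited reaction after the first injection; at least one TEAE (all, related, severe, serious) with onset from the Visit 1 injection to before the earliest of second injection, delivery, withdrawal or Day 30. Report the risk difference with a 95% Newcombe-Wilson interval. State that it is unadjusted, as in SAP 4.5, although protocol 7.3 asks for site adjustment.
2. **TEAEs by injection period within arm.** Label each period with the product injected, and show saline periods after vaccine as separate rows.

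For both, do not use the SAP 4.2 imputation to assign a period when the recorded partial date does not fix it. Show such events in a *period unknown* row, with a sensitivity count that includes them in the first period. Assign events on the day of the second injection by recorded time or, if there is none, to *period unknown*.

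Cost: SAP wording, a period variable with its date rule, and a few extra tables from data already collected.

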### 3.1 Protocol deviations

Deviations from the protocol, as continuously tracked by investigator and sponsor, will be classified as ‘minor’ or ‘major’ on a case-by-case basis. The final classification of the deviations will be decided at the final Data Review Meeting prior to database lock.

All major protocol deviations will be summarised with frequency and percentage for each category of protocol deviation.

All protocol deviations, with classification minor/major, will be presented in a listing. Further protocol deviations might be identified during the final data review meeting, but likewise certain deviations might eventually be classified as non-deviations. These decisions will be documented in the minutes from the meeting. Note that the determination of analysis sets can be made based on (subject-level) information collected during the period from randomization until 72 hours after delivery.

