**Figure 1 Flow of data for study**

### 7.3 Statistics

Details of the planned analyses will be described in the Statistical Analysis Plan (SAP), providing a detailed discussion of the analyses outlined below. Any deviations from the planned analyses will be described and justified in the final clinical study report. The SAP will be finalized before data base release and the subsequent unblinding.

All study data will be listed, and all endpoint data will be tabulated. All categorical data will be tabulated by frequency and percentage while all continuous data will be tabulated by arithmetic mean, standard deviation, and range. Data used for log-transformed analyses will also be tabulated by geometric mean and coefficient of variation. This will be relevant for the immunogenicity endpoints. Exposure to vaccinations and compliance with the vaccination schedule will be tabulated and listed. All statistical analyses will be adjusted by site, as randomisation is stratified.

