## 7.6 Analysis populations

Each subject will be classified according to the definitions below at the database release meeting. The classification and related decisions will be made by the study team and documented in the minutes from the meeting. The BIG and BPP sets refer to the children born to study participants.

- Safety analysis set (SAF): All recruited and randomized mothers who receive at least one dose of the study vaccine or placebo
- Maternal Immunogenicity Set (MIG): The subset of SAF who receive at least one dose of the study vaccine or placebo and provide an evaluable sample for analysis on any day following first exposure to study vaccine
- Maternal Per Protocol Set (MPP): The subset of MIG who receive all doses of the study vaccine or placebo and provide evaluable samples for analysis on the day of the primary immunological endpoint and do not violate the protocol up to delivery (no major protocol violation)
- Baby safety set (BSA): The babies born to mothers who have received at least one dose of the study vaccine or placebo
- Baby Immunogenicity Set (BIG): The babies born to mothers who qualify as members of the MIG analysis set
- Baby Per Protocol Set (BPP): The subset of BIG born to MPP mothers where the baby provides evaluable samples for analysis, either cord or venous blood within 72 hrs of birth

All safety analyses will be performed on the SAF and analysed according to actual treatment received (treatment arms 1 to 5). All Immunological analyses will be performed on the MIG and BIG sets. The primary immunological analysis (i.e., the immunogenicity results at delivery) will also be performed on the MPP and BPP sets. These analyses will be based on randomised treatment.

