## 7.12 Interim analysis

An early analysis of data available up to, and including, Visit 8 will be performed based on unblinded cleaned data. The analysis will include the primary immunological endpoint for IgG antibodies specific to the AlpN proteins in cord blood, the key secondary safety endpoints in all study participants (maternal participants and babies), and the secondary immunological endpoint for IgG antibodies specific to the AlpN proteins in maternal blood.

The early analysis will be conducted by an unblinded team within the CRO and the sponsor. Separate teams within the CRO and the sponsor will remain blinded until the end of the study to ensure further study execution in a blinded manner. Investigators, and site personal and study participants will remain blinded until the end of the study.

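### SAP 3.1 leaves the minor/major deviation grading, and so per-protocol membership, open until the final data review meeting, after the unblinded early analysis of the primary endpoint

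*SAP*

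**What the plan says.** **Grading.** SAP 3.1 has deviations tracked throughout and graded minor or major case by case. On timing: "The final classification of the deviations will be decided at the final Data Review Meeting prior to database lock". The meeting can do more than confirm: "Further protocol deviations might be identified during the final data review meeting, but likewise certain deviations might eventually be classified as non-deviations". Protocol 7.5 lists grounds that may make a deviation major, so the list is discretionary.

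**What the grading controls.** MPP excludes mothers with a major deviation up to delivery (SAP 3.4). BPP is restricted to babies of MPP mothers (SAP 3.7).

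**Timing of the sets and the SAP.** Protocol 7.6: "Each subject will be classified according to the definitions below at the database release meeting". SAP 3: "Each subject will be classified according to the definitions below at blinded data review meetings". SAP 3.1 adds that "determination of analysis sets can be made based on (subject-level) information collected during the period from randomization until 72 hours after delivery". Protocol 7.3: "The SAP will be finalized before data base release and the subsequent unblinding".

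**The early analysis.** Protocol 7.12: "An early analysis of data available up to, and including, Visit 8 will be performed based on unblinded cleaned data". SAP 2.4 triggers it when the last baby has completed Visit 8. SAP 6 applies the section 4 analyses to the primary endpoint, assigns the work to an unblinded team within the CRO and sponsor, and keeps separate teams blinded under a firewall charter. Protocol 2.5 says the results inform the choice of regimen.

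**The concern.** A per-protocol set guards against selective exclusion only if the exclusions are settled before anyone involved can know the results by arm. Here the early analysis covers the primary endpoint in full, at the only time point that endpoint has. The step with the most judgement in it, case-by-case grading, is nevertheless timed to the final lock rather than to this first code break.

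At stake is the credibility of the BPP analysis as a robustness check. If it is run at the early analysis and again for the final report, the two results may rest on different sets. A reader of the report could not then tell whether a regrading was made without knowledge of the results.

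**Working it through.** **1. Which sets depend on the grading**

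| Set | Uses minor/major grading? | Source |
|---|---|---|
| SAF, BSA | No: dosing of the mother | SAP 3.2, 3.5 |
| MIG | No: dosing and an evaluable sample | SAP 3.3 |
| BIG | No: mother's set membership and, in the SAP, an evaluable birth sample | Protocol 7.6; SAP 3.6 |
| MPP | Yes | SAP 3.4 |
| BPP | Yes, through MPP | SAP 3.7 |

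Protocol 7.8 bases conclusions on BIG, with BPP as a sensitivity analysis. Regrading can therefore change the BPP result but not the primary BIG comparison.

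**2. Is anything fixed before the early code break?**

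- Grading: explicitly not final until the last data review meeting.
- Sets: the protocol ties them to a database release meeting without saying which release. The SAP uses blinded meetings, plural and undated.
- SAP: final before database release and unblinding, with no separate deadline for the early analysis. The change log shows Final 4.0, dated 30-Aug-2023.

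Only the grading is expressly tied to the final lock. For the sets and the SAP, the gap is that no text ties them to the early unblinding.

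**3. The interval**

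The documents give no date for the early analysis or for lock. The visit windows give a related figure:

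- Visit 8: 0 to 3 days after delivery. Visit 11: 166 to 194 days after delivery.
- Last Visit 8 to last Visit 11, taking the same mother as last for both: 166 - 3 = 163 days to 194 - 0 = 194 days.
- At 30.44 days per month: 163/30.44 = 5.4 to 194/30.44 = 6.4 months.

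If cleaning takes 1 to 3 months before each analysis (an assumption), the gap from early analysis to lock runs from 5.4 + 1 - 3 = 3.4 to 6.4 + 3 - 1 = 8.4 months. The order of events needs only that final lock follows the last Visit 11.

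**4. Can one regrading matter?**

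The plan's rule is a 90% Newcombe-Wilson interval for the risk difference lying fully above -0.15. As a check on the calculation, exact enumeration of this rule with 60 per group and 22/23 in both groups gives 96.7% power, in line with the stated figure of above 90%.

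Lower limit = (pk - p1) - √[(pk - lk)² + (u1 - p1)²], where lk and u1 are the Wilson lower and upper limits and z = 1.645. The counts below are assumed, for illustration only.

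- Group 1, 57/60: p1 = 0.950, u1 = 0.9798, so u1 - p1 = 0.0298.
- Comparator, 53/60: pk = 0.8833, lk = 0.7981, so pk - lk = 0.0852. Lower limit = -0.0667 - √(0.0852² + 0.0298²) = -0.0667 - 0.0903 = **-0.157**. Non-inferiority is not shown.
- One comparator non-responder regraded as a major deviation, 53/59: pk = 0.8983, lk = 0.8152, so pk - lk = 0.0831. Lower limit = -0.0517 - √(0.0831² + 0.0298²) = -0.0517 - 0.0883 = **-0.140**. Non-inferiority is shown.

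One regrading can reverse a borderline BPP result. Away from the margin it need not: with a comparator at 56/60 the limit moves from -9.6 to -7.7 points, and both pass.

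**The case against.** The strongest reply is that hindsight is already controlled and little depends on BPP. Subjects are classified at blinded meetings. Separate sponsor and CRO teams stay blinded to the end of the study under a firewall charter, which is not among the documents and may say more. SAP 3.1 notes that the sets can be determined from data up to 72 hours after delivery, which matches the early-analysis cut and so permits an early freeze. BPP is a sensitivity set, and the tests are declared non-confirmatory. A final meeting is also needed anyway, because deviations at Visits 9 to 11 can only be graded later.

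Much of this stands, and it limits the point. It does not close it. The SAP permits an early freeze without requiring one, and it reserves final grading for the last meeting. The firewall separates people but sets no freeze date. SAP 3 leaves classification to the study team without saying that this excludes staff unblinded at the early analysis. The need to grade post-delivery deviations later is no reason to leave pre-delivery grading open.

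A reader might also infer more than the documents support:

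- **That the sets and the SAP are also frozen only at final lock.** The protocol's database release is ambiguous, the SAP allows earlier blinded meetings, and version 4.0 is already final. Its date cannot be placed against an undated early analysis.
- **That the primary comparison could have two versions through regrading.** It cannot, because BIG does not use the grading.
- **That the regimen is chosen on the BPP result.** Protocol 2.5 names no analysis set. SAP 6 imports section 4, so BPP is probably run at the early analysis, but as sensitivity. Regrading after a regimen has been chosen cannot alter that choice.

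**Conclusion.** The point holds for deviation grading and for the sets built on it, MPP and BPP. The stated freeze point comes after the first unblinding, and nothing in either document fixes pre-delivery grading before it. The consequence is a per-protocol sensitivity result that can still change after results by arm are known to part of the sponsor and CRO. The documents do not show that blinded staff would learn those results or that any regrading would be biased.

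The 163 to 194 days is the interval from last Visit 8 to last Visit 11, not a stated gap from early analysis to lock. The one-subject reversal is an illustration with assumed counts. The issue should be corrected because it bears on the robustness check for a regimen choice and is cheap to close, but it does not threaten the primary analysis.

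**What to change.** In SAP 3, 3.1 and 6, state that before treatment codes are released for the early analysis, staff who are still blinded sign off, under a final SAP version:

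- the grading of all deviations up to delivery, using the grounds in protocol 7.5;
- the evaluability of each birth sample;
- membership of MIG, MPP, BIG and BPP.

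Say expressly that the classifying team excludes anyone unblinded for the early analysis. Limit the final Data Review Meeting to deviations after delivery. Log any later change to the frozen grading or sets as post-unblinding, with its reason, and show BPP results both ways. Align protocol 7.3 and 7.6 so that SAP finalisation and subject classification precede the first unblinding.

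The cost is wording in the two documents and one data review meeting brought forward. By SAP 3.1's own account the sets can be determined from data up to 72 hours after delivery, so the earlier freeze needs no additional data.
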